## 2. INTRODUCTION

PF-07220060 is a selective CDK4 inhibitor that is currently being investigated in Phase 1 studies (C4391001 and C4391002) in participants with metastatic or advanced solid tumors.

### 2.1. Study Rationale

The purpose of the study will be to investigate the metabolism and excretion following a single oral administration of [ $^{14}\text{C}$ ]-PF-07220060 under fasted condition in healthy male participants. The data generated from this study will be used to assess the clearance mechanisms for PF-07220060 as well as identify metabolites that should be qualified to adhere to the ICH (M3) R2 guidance. In addition, this study will characterize the fraction of dose absorbed and bioavailability of orally administered PF-07220060 under the fasted condition, in reference to an IV infusion of [ $^{14}\text{C}$ ]PF-07220060 (given as a microtracer microdose infusion following administration of an oral unlabelled dose), and will also assess PK parameters of PF-07220060 following both oral and IV administration of [ $^{14}\text{C}$ ]PF-07220060.

This study will also evaluate sensory and taste attributes (eg, bitterness and tongue/mouth sensation) of the PF-07220060 oral suspension to guide the development of pediatric-friendly formulations.

### 2.2. Background

PF-07220060 is a selective CDK4 inhibitor that is currently being investigated in participants with metastatic or advanced solid tumors. PF-07220060 differs from currently approved dual CDK4/6 inhibitors in that it displays greater CDK4-over-CDK6 selectivity and is therefore hypothesized to drive tumor growth inhibition through greater CDK4 selectivity, while minimizing CDK6 driven hematopoietic effects. This may translate to improved efficacy and tolerability over other CDK4/6 inhibitors. The nonclinical PK/toxicokinetic, ADME properties of PF-07220060 have been evaluated in vitro and in vivo to support nonclinical safety evaluations and to assess the potential relevance to humans. The oral PK of PF-07220060 in nonclinical species indicated **CC1** oral bioavailability. The **CC1** metabolic pathways of PF-0720060 in vitro and in vivo included glucuronidation mediated by UGT2B7 and oxidation mediated by CYP3A4. Metabolites were found consistent between human in vitro system and other evaluated toxicology species (both in vitro and in vivo matrices). Renal excretion of PF-07220060 was **CC1** in rats and dogs.

The current study will investigate the absorption, metabolism and excretion of [ $^{14}\text{C}$ ]-PF-07220060 as well as the absolute bioavailability and fraction absorbed of PF-07220060 using microtracer approach in healthy male participants.

#### 2.2.1. Nonclinical Pharmacology

Details of the nonclinical pharmacology of PF-07220060 can be found in the current IB.

### 2.2.2. Nonclinical Pharmacokinetics and Metabolism

Following IV dosing in mouse, rat, and dog, PF-07220060 demonstrated CCI to CCI plasma CL (CCI% CCI% of hepatic blood flow), CCI Vss (CCI to CCI L/kg), and t1/2 values ranging from CCI to CCI hours. Single-dose PK studies with PF-07220060 in these species indicated PF-07220060 had CCI oral bioavailability (%F in the range of CCI - CCI%). In 1-month toxicity studies, systemic exposure (Cmax and AUC24) of PF-07220060 CCI CCI and CCI was observed in rats and dogs. PF-07220060 had CCI plasma protein binding (fu ranging from CCI - CCI; CCI in human plasma) and there was CCI of PF-07220060 into CCI CCI in all evaluated species (mouse, rat, dog, and human).

In vitro and in vivo (after oral administration), the CCI metabolic pathways of PF-07220060 were glucuronidation and oxidation. The metabolite profile observed in human hepatocytes was CCI that in mouse, rat, and monkey hepatocytes; there were CCI that were CCI human. The CCI metabolism pathways observed in human hepatocytes CCI in the plasma of the rat and dog toxicology species. In vitro studies indicated the metabolism of PF-07220060 was CCI UGT-mediated (CCI%) with the CCI metabolism via CYP3A4 CCI%; in addition, UGT2B7 was the CCI enzyme involved in the formation of the CCI PF-07220060 glucuronide metabolite. Renal excretion of PF-07220060 was CCI in rats and dogs. In vitro studies indicate PF-07220060 to be a substrate of CCI and CCI.

PF-07220060 has the potential for CCI of CCI in the gut and liver and to CCI at the relevant clinical exposures of CCI and 300 mg BID. PF-07220060 also has the potential for CCI CCI of CCI in the gut and liver at the relevant clinical exposures of 300 mg BID. Treatment with PF-07220060 CCI induced CCI in cryopreserved human hepatocytes. Treatment with PF-07220060 CCI or CCI at the CCI or CCI in human hepatocytes. Induction of CCI since it CCI. It is thus CCI that PF-07220060 will CCI.

Additional information on the nonclinical PK and metabolism of PF-07220060 is available in the current IB.

### 2.2.3. Nonclinical Safety

The toxicity profile of PF-07220060 was assessed in exploratory and 1-month pivotal GLP toxicity studies in rats and dogs. CCI respectively. The primary target organs identified were CCI.

PF-07220060 was assessed in a series of genetic toxicity assays. All in vitro tests were conducted with and without exogenous metabolic activation using concentrations up to those limited by cytotoxicity, insolubility, or the acceptable limits of the test system. PF-07220060 was negative for mutagenicity in both the presence and absence of metabolic activation in the GLP microbial reverse mutation assays. Additionally, PF-07220060 was negative in the exploratory in vitro micronucleus assay in TK6 cells under all test conditions. In the GLP in vivo micronucleus assessment, PF-07220060 did not induce structural chromosome aberrations or polyploidy in nucleated cells from the bone marrow of male and female rats at CCI mg/kg/day, and was therefore, not considered clastogenic in that assay. However, PF-07220060 induced small but statistically significant increases in micronucleus formation in polychromatic erythrocytes from bone marrow in male rats  $\geq$  CCI mg/kg/day and in female rats at CCI mg/kg/day. PF-07220060 is non-mutagenic (negative in Ames) and non-clastogenic (negative in chromosome aberration), PF-07220060 poses no genotoxicity risk for single-dose lifetime experimentation in healthy Participants.

PF-07220060 had minimal activity in secondary pharmacology and ex vivo safety pharmacology assays, including weak activity ( $IC_{50} > CCI \mu M$ ) toward the hERG channel. No cardiovascular effects (ECG or histopathology) were observed up to the highest dose tested (CCI mg/kg/day) in the pivotal dog study. In a conscious-telemetered dog GLP study, CCI mg/kg/day produced an CCI only after the second dose; no effects were seen after the first dose. Relative to the  $C_{max}$  at the human dose of 100 mg, the NOEL for cardiovascular effect is CCIx.

In a GLP neuropulmonary safety study in rats, PF-07220060 administration did not result in any neurofunctional or pulmonary effects up to the highest dose tested. Relative to the  $C_{max}$  at the human dose of 100 mg, the NOEL for neuropulmonary safety is CCIx.

Additional information of the nonclinical safety of PF-07220060 is available in the current IB.

#### 2.2.4. Clinical Overview

PF-07220060 is being evaluated as a single agent and in combination with ET in study C4391001 and in combination with PF-07104091 (a selective CDK2 inhibitor) in study C4391002. Included in this section are summaries of the interim results of the 2 ongoing studies.

Study C4391001 is a Phase 1/1b study of PF-07220060 in participants with advanced solid tumors with the purpose of evaluating safety, tolerability, PK, PD and anti-tumor activity of PF-07220060 as a single agent and in combination with ET. Study C4391002 is a Phase 1b/2 study of PF-07220060 and PF-07104091 in participants with mBC or other advanced solid tumors and in combination with ET (triplet combinations) in participants with metastatic/advanced mBC to evaluate the safety, tolerability, PK, PD, and antitumor activity of PF-07220060 and PF-07104091 combination.

#### 2.2.4.1. Safety Overview

As of the data cut-off date of 02 September 2022 for C4391001, a total of 66 participants have been treated with PF-07220060; 34 participants have been treated with 100, 200, 300, 400, and 500 mg BID single agent PF-07220060. Thirteen participants have been treated with 300 mg BID, and 400 mg BID PF-07220060 in combination with letrozole. Thirteen participants have been treated with 300 mg BID and 400 mg BID PF-07220060 in combination with fulvestrant. Six participants have been treated with 400 mg BID single agent PF-07220060 with food. For the C4391001 study, the monotherapy MTD for PF-07220060 was determined to be 400 mg BID. The RDE for monotherapy was determined to be 300 mg BID.

As of 02 September 2022 for C4391001, 59 (89.4%) participants reported a total of 375 all-causality TEAEs. Twenty-three participants reported all-causality Grade 3 (22 [33.3%]) or 4 (1 [1.5%]) TEAEs and 1 (1.5%) participant experienced Grade 5 all-causality TEAEs. A total of 54 (81.8%) participants reported treatment-related TEAEs during the study. 16 (24.2%) of participants reported Grade 3 treatment-related TEAEs. No Grade 4 or 5 treatment-related TEAE were reported. A total of 4 (7.3%) participants of the 55 DLT evaluable participants experienced DLTs. A total of 13 (19.7%) participants reported all-causality SAEs; of these 3 (4.5%) participants reported SAEs which were considered to be related to the study drug by the investigator. A total of 3 (4.5%) participants discontinued the study due to AEs. One (1.5%) participant discontinued study due to AEs (leukopenia and neutropenia) in 300 mg BID + Letrozole cohort that were related to treatment drug, as per the investigator.

As of the data cut-off date of 12 September 2022 for C4391002, a total of 12 participants have received PF-07220060 in combination with PF-07104091 (selective CDK2 inhibitor) across 4 dose cohorts. Of the 12 treated participants, 10 (83.3%) participants reported a total of 88 TEAEs. Most frequently reported ( $\geq 20\%$ ) all-causality were nausea (58.3%), diarrhoea, neutrophil count decreased and white blood cell count decreased (50.0% each), anaemia (41.7%), lymphocyte count decreased (33.3%), fatigue, platelet count decreased and vomiting (25.0% each). No Grade 4 TEAEs were reported. One Grade 5 TEAE of disease progression was reported during the study. A total of 10 (83.3%) of the 12 participants reported treatment-related TEAEs. Most frequently reported ( $\geq 20\%$ ) treatment-related AEs were nausea (58.3%), diarrhoea, neutrophil count decreased and white blood cell count decreased (50.0% each), lymphocyte count decreased (33.3%), anaemia, fatigue, platelet count decreased and vomiting (25.0% each). No Grade 4 or 5 treatment-related TEAEs were reported during the study. As of the data cut-off date, there was 1 DLT (Grade 3 fatigue) reported in 1 participant who received PF-07220060 300 mg BID + PF-07104091 150 mg BID.

Further details on the clinical safety information with PF-07220060 are provided in the current IB.

#### 2.2.4.2. Efficacy Overview

PF-07220060 has demonstrated early signs of anti-tumor activity in combination with ET in HR+/Her2- metastatic breast cancer patient population. Efficacy evaluation in dose expansion cohorts at RDE in combination with fulvestrant and letrozole is ongoing.

#### 2.2.4.3. Summary of PF-07220060 Pharmacokinetics in Humans

In the ongoing study C4391001, as of 30 August 2022, preliminary PK data for PF-07220060 as monotherapy and in combination with ET was available from 60 participants with advanced solid tumors. PF-07220060 was administered orally as a single agent at doses ranging from 100 to 500 mg BID, and in combination with either letrozole or fulvestrant at 300 to 400 mg BID. Available plasma concentration-time data of PF-07220060 were analyzed using noncompartmental methods.

Preliminary PK results showed that PF-07220060 was rapidly absorbed following oral administration, with median  $T_{max}$  values of 1 to 4 hours. The plasma exposure parameters of PF-07220060, including  $C_{max}$ , AUC, and  $C_{min}$ , generally increased with dose from 100 to 300 mg BID for both Cycle 1 Day 1 and Cycle 1 Day 15. The steady state exposure was increased in a less than dose proportional manner. No substantial increase in plasma exposure was observed at doses higher than 300 mg BID. Moderate accumulation of the AUC was observed following repeated BID dosing. PK of PF-07220060 as monotherapy and in combination with letrozole or fulvestrant were generally comparable. PF-07220060 exhibited moderate inter-subject variability with geometric mean CV of 11-77% for steady state  $C_{max}$  and 40-70% for  $AUC_{tau}$  in the monotherapy cohorts, 24-42% for steady  $C_{max}$  and 15-28% for  $AUC_{tau}$  in the combination with ET cohorts.

Further details on the clinical PK of PF-07220060 are provided in the current IB.

#### 2.3. Benefit/Risk Assessment

PF-07220060 will not provide any clinical benefit to healthy participants in this study. This study is designed primarily to assess human PK, absorption, metabolism, and elimination of PF-07220060 following oral and IV administrations. Participants will be expected to commit time and may experience some discomfort while undergoing study assessments. Taking into account the measures to minimize risk to participants including single dose administration and close monitoring at CRU, the potential risks associated with PF-07220060 are justified by the anticipated benefits that may be afforded by furthering the understanding of PF-07220060.

Study C4391010 is the first time that [ $^{14}C$ ]PF-07220060 will be administered to healthy adult participants, and will be the first time that IV infusions of PF-07220060 are administered to humans. Prior to this study, PF-07220060 has been administered as monotherapy or in combination with other anti-cancer agents to patients with advanced cancer at starting doses ranging from 100 mg to 500 mg BID continuously. Based on the available data from Study C4391001, the clinical safety profile favors further development of PF-07220060. Based on the results of the nonclinical toxicity studies (Section 2.2.3), the potential risk of PF-07220060 administration to healthy participants can be managed adequately, and be

mitigated with preventive measures in place that includes routine monitoring of AEs and changes in clinical laboratory test parameters for clinical management.

More detailed information about the known and expected benefits and risks and reasonably expected AEs of PF-07220060 may be found in the IB, which is the SRSD for this study. Refer to the Study Intervention(s) table in [Section 6.1](#) for a complete description of SRSDs.

### 2.3.1. Risk Assessment

Potential Risk of Clinical Significance	Summary of Data/Rationale for Risk	Mitigation Strategy
Study Intervention: PF-07220060		
Potential effects of PF-07220060 on fertility, pregnancy, and lactation.	At this time, it is not known whether PF-07220060 can cause fetal harm when administered to pregnant women. Animal reproductive studies have not been conducted with PF-07220060. It is also not known whether PF-07220060 can affect male or female fertility, or whether PF-07220060 is secreted in human milk. PF-07220060 CCI in rats and dogs on repeat administration and therefore, may potentially impact CCI	Eligibility criteria and the contraceptive lifestyle requirements (duration of caution of contraception CCI days for CCI participants ) for this protocol have been crafted to mitigate these identified potential risks. Participants will be instructed and monitored on the contraceptive requirements implemented to minimize potential risks.
Potential risks associated with PF-07220060 include the following: hematological toxicities (including anemia and neutropenia) and gastrointestinal toxicities (such as nausea, vomiting and diarrhea).	The risks are based on emerging clinical data from the ongoing clinical study C4391001 following continuous administration of PF-07220060 to advanced cancer patients at doses ranging from 100 to 500 mg BID.	The present study will only test single 100 mg oral dose of PF-07220060  AEs and clinical laboratory results will be monitored on an ongoing basis.
Study Procedures		
Exposure to radiation	This study involves using radioactive markers (labels) during oral administration in Cohort 1 and IV infusion in Cohort 2. Radiation may cause side effects including fatigue, hair loss, nausea, vomiting, low blood counts, skin problems and even cancer.	The amount of radiation administered to each participant is very low, CCI nCi, either p.o. or i.v., and below the limit suggested in the FDA Guidance that could be exempted from dosimetry calculations. Based on long-standing experience, the radiation burden will be below 0.1 mSv, ie, ICRP Category I, trivial risk of health damage due to the exposure to ionising radiation.

### 2.3.2. Benefit Assessment

PF-07220060 will not provide any clinical benefit to healthy participants in this study. This study is designed primarily to further the understanding of human PK, absorption, metabolism, and elimination of PF-07220060 following oral and IV administrations.

### 2.3.3. Overall Benefit/Risk Conclusion

Based on available clinical data with PF-07220060 (Section 2.2.4 and current IB), a single 100 mg oral dose (Cohort 1), and a single 100 mg oral dose followed by  $\text{CCl}_4$   $\mu\text{g}$  IV dose (Cohort 2) are anticipated to be safe and well tolerated. Each participant will be exposed to approximately  $\text{CCl}_4$  nCi over the entire study duration, which includes dosing [ $^{14}\text{C}$ ]PF-07220060 in Cohort 1 and Cohort 2. This is classed as a microtracer dose, without any anticipated risk to study participants.

Based on the profile of PF-07220060 observed in nonclinical and clinical studies to date, and the measures taken as part of the study to minimize risk to study participants, the potential risks associated with PF-07220060 are justified by the anticipated benefits that may be afforded by furthering the understanding of PF-07220060.

### 3. OBJECTIVES AND ENDPOINTS

Objectives	Endpoints
Primary:	Primary:

 
To characterize the rate and extent of excretion of total radioactivity following administration of a single oral dose of [C]PF-07220060.
 
To characterize the metabolic profile for PF-07220060 and identify the circulating and excreted metabolites of PF-07220060 following administration of a single oral dose of [C]PF-07220060.
 
	
 
Mass Balance: Cumulative recovery (%) of radioactivity in urine and feces (adjusted for vomitus, if any), expressed as a percent of total oral radioactive dose administered (quantification by AMS).
 
Metabolic profiling/metabolite identification and determination of relative abundance of [C]PF-07220060 and its metabolites in plasma, urine and feces, if possible (Cohort 1).
 

Secondary:	Secondary:

 
To determine the absolute oral bioavailability (F) of PF-07220060 from a single oral dose of PF-07220060 under fasted conditions followed by a single IV microdose of [C]PF-07220060.
 
To determine the fraction of PF-07220060 dose absorbed (Fa) from a single oral dose of [C]PF-07220060 under fasted conditions.
 
To determine the safety and tolerability of PF-07220060, administered as a single oral dose of [C]PF-07220060 or a single oral dose of PF-07220060 followed by administration of a single IV dose of [C]PF-07220060.
 
	
 
The ratio of dose-normalized plasma AUCinf of oral PF-07220060 (LCMS) and IV [C]PF-07220060 (HPLC-AMS) [Cohort 2 only].
 
Fa calculated from the ratio of total recovered radioactivity [C] in urine following single dose administration of [C]PF-07220060 orally in Cohort 1 and via IV infusion in Cohort 2 (quantification by AMS).
 
AE monitoring, physical examination, clinical laboratory measurements, vital signs and 12-lead ECGs.
 

Tertiary/Exploratory:	Tertiary/Exploratory:

 
To characterize the metabolic profile and identify the circulating and excreted metabolites of PF-07220060 following administration of a single oral dose of PF-07220060 followed by administration of a single IV dose of [C]PF-07220060 (as needed).
 
To determine the plasma PK parameters of a single oral dose of PF-07220060 following administration as a single oral dose of [C]PF-07220060 or a single oral dose of PF-07220060 followed by administration of a single IV microdose of [C]PF-07220060.
 
To determine plasma PK parameters of [C]PF-07220060 following administration
 
	
 
Contingent metabolic profiling/metabolite identification and determination of relative abundance of [C]PF-07220060 and the metabolites of [C]PF-07220060 in plasma, urine and feces, if possible (Cohort 2).
 
Plasma PK parameters of PF-07220060 from LCMS analyses (Cohort 1 and Cohort 2): 
 
AUClast, Cmax, Tmax.
 
If data permits: AUCinf, t1/2, Vz/F, CL/F.
 
 
 
Plasma PK parameters of [C]PF-07220060 from HPLC-AMS analyses (Cohort 2): 
 
AUClast, Cmax, Tmax.
 
 
 

PFIZER CONFIDENTIAL

CT02-GSOP Clinical Pharmacology Protocol Template (14 April 2023)

Objectives	Endpoints
of a single IV microdose of [  C]PF-07220060.	
 
If data permits: AUCinf, t1/2, CL, Vss.
 

 
To determine the urine PK parameters of PF-07220060 following administration as a single oral dose of [C]PF-07220060 (if measured)
 
	
 
Urine PK parameters of PF-07220060 from LCMS (Cohort 1): 
 
CLR, Ae(∞), and Ae%.
 
 
 


 
To determine plasma PK parameters of total radioactivity following administration of a single oral dose of [C]PF-07220060.
 
	
 
Plasma PK parameters of total radioactivity [C] from AMS analyses (Cohort 1): 
 
AUClast, Cmax, Tmax of total radioactivity.
 
If data permit: AUCinf, t1/2.
 
 
 

 
To determine plasma PK parameters of total radioactivity following a single oral dose of PF-07220060 followed by administration of a single IV dose of [C]PF-07220060 (as needed).
 
	
 
Plasma PK parameters of total radioactivity [C] from AMS analyses (Cohort 2): 
 
AUClast, Cmax, Tmax of total radioactivity.
 
If data permit: AUCinf, t1/2.
 
 
 

 
To explore the impact of pharmacogenomics on absorption, distribution, metabolism and excretion of [C]-PF-07220060 and the absolute bioavailability and fraction absorbed of PF-07220060.
 
	
 
Allelic variants of drug metabolizing enzymes and transporters
 

 
To evaluate the sensory and taste attributes of the PF-07220060 oral suspension in healthy participants under fasted conditions.
 
	
 
Taste Assessment Survey Scoring Metrics: mouthfeel, bitterness, sweetness, sourness, saltiness, tongue/mouth burn, throat burn, and overall liking.
 

## 4. STUDY DESIGN

### 4.1. Overall Design

This study will be a Phase 1, open-label, parallel-group, single-dose study of PF-07220060 to characterize the metabolic profile and routes of excretion for oral [C]PF-07220060 and to evaluate F of PF-07220060 and Fa of [C]PF-07220060, in reference to IV microtracer [C]PF-07220060 in fasted healthy male participants.

In order to achieve sufficient bioanalytical sensitivity for the microtracer dose and differentiate the plasma concentrations resulting from the radiolabeled IV dose and those resulting from the oral dose, the ultra-sensitive AMS method will be used to quantify plasma concentrations of radiolabeled parent drug as well as total radioactivity [C] derived from the microtracer dose based on measurement of C. Theoretically, Fa would be expected to be greater than F. In the event that F is estimated to be greater than Fa (because of the possibility that F is likely to be more precisely estimated due to analytical techniques), the greater of the

2 values will be used to represent the fraction of PF-07220060 absorbed. PF-07220060 will be considered highly permeable if either F or  $F_a$  is greater than 0.9 (as per BCS guidance).

Approximately 6 healthy adult male participants will be enrolled in each of the 2 cohorts. Participants in Cohorts 1 and 2 will receive treatment regimen A and B, respectively. If there are participants who withdraw or discontinue treatment and are considered to be non-evaluable with respect to the primary and secondary PK objective(s), additional participants can be enrolled at the discretion of the investigator upon consultation with the sponsor. The SoA for Cohorts 1 and 2 (Table 1 and Table 2, respectively) describes procedures/assessments to be conducted from check-in to the CRU on Day -1 up to the discharge day occurring between Days 5 to 14 of each cohort.

Screening will occur within 28 days of the first dose of investigational product. All participants will provide informed consent and undergo screening evaluations to determine their eligibility. Eligible participants will be admitted to the CRU on Day -1. Prior to dosing in both Cohorts, pre-dose urine samples must be collected within 24 hrs prior to dosing and pre-dose fecal samples must be collected within 48 hrs prior to dosing (may be collected at home). The last collected fecal sample will be used as pre-dose sample and all previous pre-dose samples will be destroyed.

Regardless of whether or not the discharge criteria for each cohort have been met, no participant will be confined beyond Day 14 for both Cohorts. The maximum total in-house participation time for each participant in this study is approximately 15 days and 14 nights. Participants will have a follow-up phone call at 28-35 days after the last dose of study intervention.

**Cohort 1:** A single oral dose of 100 mg  $^{14}\text{C}$ -labeled PF-07220060 containing approximately  $^{14}\text{C}$  (ie, "lightly radiolabeled" or microtracer [ $^{14}\text{C}$ ]PF-07220060) will be administered following an overnight fast of at least 10 hours. Dosing will involve administration of multiple rinses of the dosing container, and an assessment of the residual radioactivity on the dosing container will be required to be assessed and documented in the study CRF (see also Section 6.1.1). Blood, urine, feces, and vomitus (if any) samples will be collected as detailed in the SoA up until the discharge day occurs between Days 5 to 14. Discharge may occur for participants who meet at least one of the 2 radioactivity recovery criteria or reached the maximum duration of in-house stay. The discharge criteria are: (1) at least 90% of the administered radioactive dose has been recovered in urine+feces+vomit (if any), (2) <1% of the administered radioactive dose has been recovered in urine+feces during 24-hour intervals over 2 consecutive days, or (3) the participant has reached Day 14. Each bowel movement must be collected, and time and date must be recorded. If an individual participant has not experienced a bowel movement within 36 hrs of their previous bowel movement, fluid intake should be increased and administration of a mild laxative (eg, prune juice or a mild stool softener) should be implemented, with the goal to facilitate at least once daily bowel movement. The use of the laxative should be recorded in the CRF.

Vomit, if any, will be collected in full during the  $^{14}\text{C}$  hours after oral dosing in Cohort 1 and will be required to be prospectively tested for recovered radioactivity. For emesis that occurs

after [REDACTED] hours up to [REDACTED] hours post dose, samples will be collected in full and stored for potential reflex testing for recovered radioactivity. The time and date of any vomiting event within the first [REDACTED] hours post-dose must be recorded. Participants who experience emesis following oral dosing will not necessarily be excluded from analysis (see [Section 9.3](#) for additional details on evaluable participants).

**Cohort 2:** A single oral dose of 100 mg unlabeled PF-07220060 will be administered following an overnight fast of at least 10 hours followed by an IV microtracer microdose of [REDACTED] µg [C]PF-07220060 containing approximately [REDACTED] nCi C at the approximate time of anticipated peak plasma concentration (Tmax). The C IV dose will be administered as an infusion over approximately 30 minutes starting at approximately 2 hour (anticipated Tmax) after the administration of the unlabeled oral dose. Blood, urine, feces, and vomitus (if any) samples will be collected as detailed in the [SoA](#) up until the discharge day occurs between Days 5 to 14. The duration of confinement for Cohort 2 will equal the longest individual participant duration of confinement in Cohort 1 so that the duration of urine sample collections over the periods is consistent to aid in accurate estimation of the Fa.

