### 5.3.2. Meals and Dietary Restrictions

- Participants must abstain from all food and drink (except water) at least 4 hours prior to any safety laboratory evaluations and 10 hours prior to the collection of the predose PK sample on Day 1. No food will be allowed for at least 4 hours postdose on Day 1.
- On Day 1, water will be permitted until 1 hour prior to study intervention administration. Water may be consumed without restriction beginning 1 hour after dosing. Noncaffeinated drinks (except grapefruit or grapefruit-related citrus fruit juices—see below) may be consumed with meals and the evening snack.
- Lunch will be provided approximately 4 hours after dosing on Day 1.
- Dinner will be provided approximately 9 to 10 hours after dosing on Day 1.
- An evening snack may be permitted.
- Participants will refrain from consuming red wine, grapefruit, or grapefruit-related citrus fruits (eg, Seville oranges, pomelos, fruit juices) from 7 days prior to the first dose of study intervention until collection of the final PK blood sample.
- While participants are confined, their total daily nutritional composition should be approximately 55% carbohydrate, 30% fat, and 15% protein. The daily caloric intake per participant should not exceed approximately 3200 kcal.
- Participants will be asked to abstain from consuming indigestible materials (eg, corn, nuts, etc) for 2 days prior to dosing and for the duration of the study in order to facilitate ease of fecal homogenization.
- If an individual participant has not experienced a bowel movement in any 36 hour period post-dose, fluid intake should be increased and administration of a mild laxative (eg, prune juice or a mild stool softener) should be implemented.
- In Cohort 1, participants will be confined from the evening prior to the first dose until at least the morning of Day **CC1** **CC1** hours postdose). If necessary, urine and/or fecal

collections will continue beyond Day **06** until Day 14 or until one of the following conditions are met:

- The amount of cumulative radioactivity recovered in excreta is at least 90% of administered radioactivity, or
- Less than 1% of the administered radioactivity has been recovered in excreta from 2 consecutive days (ie, total for urine + feces should <1% on 2 consecutive days).

The duration of confinement for Cohort 2 participants will equal the longest individual participants duration of confinement in Cohort 1.

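### Discharge criterion 2 can be met by two stool-free days when urine is also below 1%, so Cohort 1 collection may stop before faecal excretion is complete

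*Protocol*

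**What the plan says.** Protocol 4.1 lists three discharge criteria for Cohort 1: at least 90% of the radioactive dose recovered, less than 1% "of the administered radioactive dose has been recovered in urine+feces during 24-hour intervals over 2 consecutive days", or Day 14 reached. The synopsis says the same. Any one suffices, and the wording is permissive: "Discharge may occur for participants who meet at least one of the 2 radioactivity recovery criteria" or who reach the maximum stay. Discharge falls between Days 5 and 14.

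Protocol 5.3.2 restates the second criterion as "Less than 1% of the administered radioactivity has been recovered in excreta from 2 consecutive days", and explains it as "total for urine + feces should <1% on 2 consecutive days". There, collections beyond the minimum stay run to Day 14 or until a recovery condition is met. The Schedule of Activities collects feces in 24-hour intervals up to discharge.

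Section 4.1 also contains a safeguard. "If an individual participant has not experienced a bowel movement within 36 hrs of their previous bowel movement", fluids are increased and a mild laxative is given, "with the goal to facilitate at least once daily bowel movement". Section 5.3.2 repeats the step, and exclusion criterion 2 removes people with irregular bowel movements.

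No section of the protocol or SAP says how an interval without stool counts toward criterion 2.

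**The concern.** Criterion 2 is there to show that excretion has effectively finished. Urine is produced every day, so a low urinary figure carries information. Feces are different: a day without stool contributes 0% however much radioactivity is still in the bowel. When urine is also low, two such days look the same as completed excretion.

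Cumulative recovery in urine and feces is a primary endpoint, with about 6 participants in the cohort. Stool passed after discharge is never collected, so for a mainly faecally excreted dose that participant's recovery is understated and the urine/feces split is shifted toward urine. Discharge on these terms follows the protocol, so it is not a deviation that would remove the participant from the mass balance analysis set. The truncated value would enter the summary in SAP 6.1.1 with no required flag. Protocol 4.2 says metabolite half-lives are unknown and that the extended stay exists to let slower metabolites be excreted. An early stop on empty intervals would work against that purpose.

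**Working it through.** The plan states no figure to reproduce here. Three checks were made.

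**1. Time available to the laxative step.** Take 72–96 h and 96–120 h as the two empty intervals. The step starts 36 h after the last stool.
- Last stool at 72 h: start at 72 + 36 = 108 h, so in force for 120 − 108 = 12 h before the second interval closes.
- Last stool at 48 h: start at 48 + 36 = 84 h, so in force for 120 − 84 = 36 h.

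The step therefore has 12 to 36 h to act. It makes two empty intervals less likely but does not rule them out.

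**2. Illustrative size.** Assumptions, none of them from the documents: the whole dose is excreted, 10% in urine and 90% in feces; both are first order with the same half-life h; stool at 72 h clears everything due by then; no further stool until after 120 h; discharge at 120 h. Day 14 is 312 h.

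cum(t) = 1 − 2^(−t/h). Recovered at discharge = cum(72) + 0.10 × [cum(120) − cum(72)].

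| | h = 24 h | h = 36 h |
|---|---|---|
| Urine, 72–96 h | 0.62% | 0.93% |
| Urine, 96–120 h | 0.31% | 0.58% |
| Two-day urine total | 0.94% | 1.51% |
| Criterion 2, 1% read per day | met | met |
| Criterion 2, 1% read as two-day total | met | not met |
| Recovered at 120 h | 87.5 + 0.94 = 88.4% | 75.0 + 1.51 = 76.5% |
| cum(312) | 100.0% | 99.8% |
| Shortfall, participant | 11.6 points | 23.3 points |
| Shortfall, mean of six | 11.6 / 6 = 1.9 | 23.3 / 6 = 3.9 |

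Both recoveries are below 90%, so criterion 1 is not met in either case.

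**3. How far this depends on the assumptions.**
- *Urine share, 1% read per day.* The first interval carries 6.25% of the urinary amount at h = 24 h and 9.25% at h = 36 h. Criterion 2 is met only for urine shares below 1/0.0625 = 16% and 1/0.0925 = 10.8% respectively.
- *Timing.* One day earlier (empty intervals 48–72 h and 72–96 h), a 10% share with h = 24 h gives 0.10 × (25 − 12.5) = 1.25% in the first interval, so criterion 2 is not met.
- *Shorter half-life.* cum(72) reaches 90% when h = 72 / log2(10) = 21.7 h. At or below that, criterion 1 is already met by the stool at 72 h and the loss is under 10 points. At h = 12 h it is 0.90 × 1.56 = 1.4 points.
- *Earlier discharge with little urinary excretion.* Assume 95% of dose excreted in total, 5% in urine, a 12 h faecal lag, last stool at 48 h and discharge at 96 h. The faecal dose not recovered is 0.90 × 2^(−36/h), about 11%, 32% and 45% for faecal half-lives of 12, 24 and 36 h. The size can therefore also exceed the figures in the table.

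**The case against.** A reader might infer that two stool-free days meet the criterion automatically. They do not. The criterion sums urine and feces, so urine must be below 1% as well, and several plausible combinations fail on urine alone.

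A reader might also infer that the laxative step has only about 12 hours to work. That is the minimum, and the range is 12 to 36 h.

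The other safeguards are real. Irregular bowel habit is an exclusion, discharge is permissive in 4.1, and it cannot occur before Day 5. A volunteer with regular bowels would have to go 48 h or more without stool despite the laxative step, and the site would then have to discharge him. The 36 h case is near the edge: about 16% of the dose would still be unexcreted at 96 h, whereas 4.2 sets the minimum stay by when circulating parent drug should fall below quantification. That benchmark concerns parent drug in plasma, however, and 4.2 itself allows for slower metabolites.

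No hypothesis is tested. Recovery is listed individually, the profiles shown are individual and median, and stool times are recorded, so a truncated participant could be found by someone who looked, and a median is less affected than a mean.

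All of this stands, and it lowers both the probability and the consequence. None of it changes how an empty interval is counted, and neither document requires the case to be identified.

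**Conclusion.** The gap holds in limited form. As written, criterion 2 can be met by two stool-free intervals when urinary recovery is also below 1%, with no stool requirement and no recovery floor behind it. The event is unlikely. If it occurs with a mainly faecally excreted dose, that participant's primary recovery is biased downward and the urine/feces split is distorted.

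The illustrated effect on a six-person mean is conditional, not a forecast. It rests on an assumed 10% urine share, common half-lives of 24 or 36 h, and exactly one affected participant. The 36 h figure also needs the 1% to be read per day. Other inputs move the size in either direction. The documents do not support a claim that recovery will be understated, only that the stopping rule permits it.

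A second ambiguity is confirmed: 4.1 and 5.3.2 do not settle whether 1% applies to each day or to the two-day total, and in the 36 h case that decides whether the criterion is met. The point is worth correcting mainly because the remedy is cheap and the endpoint is primary.

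**What to change.** In the synopsis, 4.1 and 5.3.2:
- State that a 24-hour interval counts toward criterion 2 only if at least one stool was collected in it.
- State whether the 1% limit applies to each of the two days or to their total, in the same words in all three places.
- Keep the Day 14 maximum as it is.

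The cost is protocol wording and an occasional longer stay, never beyond Day 14. Because Cohort 2 confinement equals the longest individual stay in Cohort 1, Cohort 2 may also stay longer.

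If an amendment is no longer possible, the clinical study report should flag any participant discharged under criterion 2 without stool in the qualifying intervals.
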